9.1.3 Serious Adverse Events

A serious adverse event is defined as an adverse event that meets at least 1 of the following serious criteria (unless it meets the definition of a Disease Related Event as defined in [Section 9.1.1](#)):

- fatal
- life threatening (places the subject at immediate risk of death)
- requires in-patient hospitalization or prolongation of existing hospitalization
- results in persistent or significant disability/incapacity
- congenital anomaly/birth defect
- other medically important serious event

A disease related event as listed in [Appendix D](#) is to be reported as a serious adverse event if

- the subject's pre-existing condition becomes worse than what the investigator would consider typical for a patient with the same underlying condition, or
- if the investigator believes a causal relationship exists between the investigational medicinal product(s)/protocol-required therapies and the event,
- and the event meets at least 1 of the serious criteria above.

An adverse event would meet the criterion of "requires hospitalization", if the event necessitated an admission to a health care facility (eg, overnight stay), and/or treatment that would not have been appropriate in the physician's office or outpatient setting. Complications that occur during hospitalization are an adverse event. If a complication prolongs a hospitalization or fulfills any other serious criteria, the event is serious. When in doubt as to whether "hospitalization" occurred or was necessary, the adverse event is to be considered serious. Hospitalization for elective treatment of a pre-existing condition that did not worsen from baseline is not considered an adverse event.

The term disability means a substantial disruption of a person's ability to conduct normal life functions. The definition is not intended to include experiences of relatively minor medical significance such as uncomplicated headache, nausea, vomiting, diarrhea, influenza, and accidental trauma (eg, sprained ankle) which may interfere with or prevent everyday life functions but do not constitute a substantial disruption.

If an investigator considers an event to be clinically important, but it does not meet any of the serious criteria, the event could be classified as a serious adverse event under the criterion of "other medically important serious event". Examples of such events could include invasive or malignant cancers, intensive treatment in the emergency room or at

home for allergic bronchospasm, convulsions, or blood dyscrasias that do not result in hospitalization, or development of drug dependency or drug abuse.

9.2 Safety Event Reporting Procedures

9.2.1 Reporting Procedures for Disease Related Events

The investigator is responsible for ensuring that all Disease Related Events observed by the investigator or reported by the subject that occur after the first dose of protocol-required therapies through the SFU visit are recorded using the Event eCRF as a disease-related event.

All serious disease-related events will be recorded and reported to the sponsor or designee within 24 hours. The investigator will submit any updated serious disease-related event data to the sponsor within 24 hours of it being available.

Disease-related events assessed by the investigator to be more severe than expected and/or related to the investigational medicinal product(s)/study treatment/protocol-required therapies, and determined to be serious, must be recorded on the Event CRF as serious adverse events, and reported per [Section 9.2.2.2](#).

Additionally, the investigator is required to report a fatal Disease Related Event on the Event eCRF.

9.2.2 Adverse Events

9.2.2.1 Reporting Procedures for Adverse Events That Do not Meet Serious Criteria

The investigator is responsible for ensuring that all adverse events observed by the investigator or reported by the subject that occur after protocol-required therapies through the SFU visit are reported using the Event eCRF. Adverse events related to obligatory pre-medication as well as adverse events related to study procedures during the screening period will be reported on the Event eCRF. If any other anti-leukemic therapy is started within 30 days after last administration of blinatumomab, subsequently only adverse events assessed as being related to blinatumomab will be reported. During the long-term follow-up period, only adverse events assessed as related to blinatumomab or study procedures will be recorded.

The investigator must assign the following adverse event attributes:

- Adverse event diagnosis or syndrome(s), if known (if not known, signs or symptoms),
- Dates of onset and resolution (if resolved),
- Severity [and/or toxicity per protocol],

- Assessment of relatedness to blinatumomab, and
- Action taken.

The adverse event grading scale used will be the CTCAE version 4.03. The grading scale used in this study is described in [Appendix A](#). The investigator must assess whether the adverse event is possibly related to blinatumomab. This relationship is indicated by a “yes” or “no” response to the question: Is there a reasonable possibility that the event may have been caused by investigational product (blinatumomab) or other protocol-required therapies?

The investigator must assess whether the adverse event is possibly related to any study-mandated activity (eg, administration of investigational product, protocol-required therapies, device(s) and/or procedure (including any screening procedure(s))). This relationship is indicated by a “yes” or “no” response to the question: “Is there a reasonable possibility that the event may have been caused by a study activity (eg, administration of investigational product, protocol-required therapies, device(s)), and/or procedure”?

The investigator is responsible for reviewing laboratory test results and determining whether an abnormal value in an individual study subject represents a clinically significant change from the subject’s baseline values. In general, abnormal laboratory findings without clinical significance (based on the investigator’s judgment) are not to be recorded as adverse events. However, laboratory value changes that require treatment or adjustment in current therapy are considered adverse events. Where applicable, clinical sequelae (not the laboratory abnormality) are to be recorded as the adverse event.

The Investigator is expected to follow reported adverse events until stabilization or reversibility.

9.2.2.2 Reporting Procedures for Serious Adverse Events

The investigator is responsible for ensuring that all serious adverse events observed by the investigator or reported by the subject that occur during the entire study period including the screening period (from the signing of the informed consent) through the SFU visit are recorded in the subject’s medical record and are submitted to Amgen. All serious adverse events must be submitted to Amgen within 24 hours following the investigator’s knowledge of the event via the Event CRF.

Approved

If the electronic data capture (EDC) system is unavailable to the site staff to report the serious adverse event, the information is to be reported to Amgen via an electronic Serious Adverse Event Contingency Report Form within 24 hours of the investigator's knowledge of the event. See [Appendix B](#) for a sample of the Serious Adverse Event Worksheet/electronic Serious Adverse Event Contingency Report Form. For EDC studies where the first notification of a Serious Adverse Event is reported to Amgen via the electronic Serious Adverse Event Contingency Report Form, the data must be entered into the EDC system when the system is again available.

The investigator must assess whether the serious adverse event is possibly related to any study-mandated activity or procedure. This relationship is indicated by a "yes" or "no" response to the question: "Is there a reasonable possibility that the event may have been caused by a study activity/procedure"?

The investigator is expected to follow reported serious adverse events until resolution, stabilization of the condition, or until the subject is lost to follow-up.

New information relating to a previously reported serious adverse event must be submitted to Amgen. All new information for serious adverse events must be sent to Amgen within 24 hours following knowledge of the new information. The investigator may be asked to provide additional follow-up information, which may include a discharge summary or extracts from the medical record. Information provided about the serious adverse event must be consistent with that recorded on the Event eCRF.

If a subject is permanently withdrawn from protocol-required therapies because of a serious adverse event, this information must be submitted to Amgen.

To comply with worldwide reporting regulations for serious adverse events, the treatment assignment of subjects who develop serious, unexpected, and related adverse events may be unblinded by Amgen before submission to regulatory authorities

Amgen will report serious adverse events and/or suspected unexpected serious adverse reactions as required to regulatory authorities, investigators/institutions, and IRBs/IECs in compliance with all reporting requirements according to local regulations and good clinical practice.

The investigator is to notify the appropriate IRB/IEC of serious adverse events occurring at the site and other adverse event reports received from Amgen, in accordance with local procedures and statutes.

9.2.2.3 Reporting Serious Adverse Events After the Protocol-required Reporting Period

There is no requirement to monitor study subjects for serious adverse events following the protocol-required reporting period or after end of study. However, these serious adverse events can be reported to Amgen. In some countries, investigators are required to report serious adverse events that they become aware of after end of study. If serious adverse events are reported, the investigator is to report them to Amgen within 24 hours following the investigator's knowledge of the event.

Serious adverse events reported outside of the protocol-required reporting period will be captured within the safety database as clinical trial cases for the purposes of expedited reporting.

9.2.2.4 Drug-induced Liver Injury Reporting and Additional Assessments Reporting

To facilitate appropriate monitoring for signals of DILI, cases of concurrent AST or ALT and TBL and/or INR elevation according to the criteria specified in [Section 6.7](#) require the following:

The event is to be reported to Amgen as a serious adverse event within 24 hours of discovery or notification of the event (ie, before additional etiologic investigations have been concluded).

The appropriate CRF (eg, Adverse Event CRF) that captures information necessary to facilitate the evaluation of treatment-emergent liver abnormalities is to be completed and sent to the Amgen.

Other events of hepatotoxicity and potential DILI are to be reported as serious adverse events if they meet the criteria for a serious adverse event defined in [Section 9.1.3](#).

See [Appendix B](#) for a sample of the Serious Adverse Event Worksheet/eSAE Contingency Report Form. For EDC studies where the first notification of a serious adverse event is reported to Amgen via the eSAE Contingency Report Form, the data must be entered into the EDC system when the system is again available.

The investigator must assess whether the serious adverse event is possibly related to any study-mandated activity or procedure. This relationship is indicated by a "yes" or "no" response to the question: "Is there a reasonable possibility that the event may have been caused by a study activity/procedure"?

Approved

The investigator is expected to follow reported serious adverse events until stabilization or reversibility.

New information relating to a previously reported serious adverse event must be submitted to Amgen. All new information for serious adverse events must be sent to Amgen within 24 hours following knowledge of the new information. The investigator may be asked to provide additional follow-up information, which may include a discharge summary or extracts from the medical record. Information provided about the serious adverse event must be consistent with that recorded on the Event CRF.

9.2.2.5 Serious Adverse Events That are NOT TO BE Reported in an Expedited Manner

Serious disease related events are not subjected to report individually in an expedited manner by Amgen unless it meets the criteria listed in [Section 9.1.3](#). A Data Review Team (DRT) will be used to monitoring the benefit/risk of such events.

9.3 Pregnancy and Lactation Reporting

If a female subject becomes pregnant, or a male subject fathers a child, while the subject is taking blinatumomab, report the pregnancy to Amgen as specified below.

In addition to reporting any pregnancies occurring during the study, investigators should monitor for pregnancies that occur within 48 hours after the last dose of blinatumomab.

The pregnancy should be reported to Amgen Global Patient Safety within 24 hours of the investigator's knowledge of the event of a pregnancy. Report a pregnancy on the Pregnancy Notification Worksheet ([Appendix C](#)). Amgen Global Patient Safety will follow-up with the investigator regarding additional information that may be requested.

If a female subject becomes pregnant during the study, the investigator should attempt to obtain information regarding the birth outcome and health of the infant. If a male subject's female partner becomes pregnant, the investigator should discuss obtaining information regarding the birth outcome and health of the infant from the pregnant partner.

If the outcome of the pregnancy meets a criterion for immediate classification as a Serious Adverse Event (eg, female subject experiences a spontaneous abortion, stillbirth, or neonatal death or there is a fetal or neonatal congenital anomaly) the investigator will report the event as a Serious Adverse Event.

If a female breastfeeds while taking protocol-required therapies report the lactation case to Amgen as specified below.

If a lactation case occurs while the female subject is taking protocol-required therapies report the lactation case to Amgen as specified below.

In addition to reporting a lactation case during the study, investigators should report lactation cases that occur after the last dose of protocol-required therapies through 48 hours.

Any lactation case should be reported to Amgen Global Patient Safety within 24 hours of the investigator's knowledge of event. Report a lactation case on the Lactation Notification Worksheet ([Appendix C](#)). Amgen Global Patient Safety will follow-up with the investigator regarding additional information that may be requested.

10. STATISTICAL CONSIDERATIONS

10.1 Study Endpoints, Analysis Sets, and Covariates

10.1.1 Study Endpoints

10.1.1.1 Primary Endpoint

- CR/CRh* rate within 2 cycles of treatment with blinatumomab

10.1.1.2 Secondary Endpoints

- CR rate within 2 cycles of treatment with blinatumomab
- CR/CRh*/CRi (complete remission with incomplete hematological recovery) rate within 2 cycles of treatment with blinatumomab
- PK parameters
- OS
- RFS
- MRD response rate within 2 cycles of treatment with blinatumomab
- Proportion of subjects undergoing alloHSCT among those who achieved CR/CRh* after treatment with blinatumomab
- 100 day mortality after alloHSCT
- Time to a 10 point decrease from baseline in global health status/Quality of Life (QoL) using the EORTC QLQ-C30.

10.1.1.3 Safety Endpoints

- Overall incidence and severity of adverse events
- Incidence of anti-blinatumomab antibody formation

10.1.1.4 Exploratory Endpoints

- Neurological adverse events
- Quantification and characterization of peripheral blood lymphocyte subsets
- Quantification and characterization of serum cytokines and chemokines

Approved

10.1.2 Analysis Sets

The statistical analysis will be based on the following study populations:

- Primary Analysis Set (PAS): All enrolled subjects who received at least one infusion of blinatumomab.
- Safety Analysis Set (SAS): All enrolled subjects who received at least 1 infusion of blinatumomab. The definition is the same as primary analysis set.
- Pharmacokinetic Analysis Set (PKS): All subjects who received any infusion of blinatumomab and had at least 1 PK sample collected will be included in the PK analysis set. These subjects will be evaluated for PK unless significant protocol deviations affect the data analysis or if key dosing, dose interruption, or sampling information is missing.

The primary analysis of efficacy and safety will be performed on PAS and SAS separately.

10.1.3 Covariates and Subgroups

The following covariates may be used to examine efficacy and/or safety in subgroups or covariates analyses:

- Sex (female vs male)
- Age (< 35 vs ≥ 35 to 55 vs ≥ 55)
- Prior salvage therapy (yes vs no)
- Prior alloHSCT (yes vs no)
- Bone marrow blast at baseline (< 50% vs ≥ 50%)
- Disease status (primary refractory vs first relapse vs second or later relapse)
- Refractory to last previous therapy (yes vs no)

10.2 Sample Size Considerations

The overall sample size of 120 subjects, calculated using the exact method for a single proportion, was estimated in order to ensure 90% power to detect a significant difference in terms of CR/CRh* rate between historical control with 30% CR/CRh* rate and blinatumomab assuming 45% CR/CRh* rate in the alternative hypothesis, at the 2.5% one-sided significance level.

[Table 12](#) lists the exact 95% confidence intervals of various observed clinically meaningful CR/CRh* rates by using single-agent blinatumomab given to 120 subjects.

Table 12. 95% Confidence Intervals of Various Observed CR/CRh* Rates in Blinatumomab Administered to 120 Subjects

Observed CR/CRh* rate	Exact 95% CI for CR/CRh* rate
40%	[31.1%, 49.3%]
45%	[35.9%, 54.3%]
50%	[40.7%, 59.2%]

10.3 Planned Analyses

10.3.1 Interim Analyses

The Interim Analysis Set is defined as the first 90 subjects (75% of the expected total) who have had the opportunity to be treated with at least 2 cycles of blinatumomab and to finish the SFU visit (if subjects discontinue treatment after 2 cycles), or have discontinued the treatment of blinatumomab and complete the SFU visit, whichever occurs first. The interim analysis will assess blinatumomab efficacy and safety and will be based on this Interim Analysis Set. The efficacious benefit assessment will be based on an O'Brien-Fleming alpha spending function with the critical boundary 42.2% at the interim analysis and 39.2% at the primary analysis in CR/CRh* rate. If the interim analysis shows a statistically efficacious benefit assessment and an overall benefit-risk analysis is promising, then the interim analysis will become the primary analysis of this study. In addition, the study will still continue its enrollment until 120 subjects are enrolled and continue to complete the protocol specified procedures.

Additional ad hoc Interim Analyses may be performed. Pharmacokinetic samples collected at specific timepoints may be analyzed and reported. The purpose of this additional interim data analyses is to provide descriptive analyses of PK, safety, and efficacy information (including 95% confidence intervals) for regulatory submissions and interactions.

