2.5.2 Study MT103-211

Study MT103-211 is an open-label, multicenter, global, single-arm, phase 2 study in high-risk adult subjects with Ph-negative B-precursor relapsed/refractory ALL, specifically that have 1) relapsed or refractory ALL with first remission duration less than or equal to 12 months in first salvage or 2) relapsed or refractory ALL after first salvage therapy or 3) relapsed or refractory ALL within 12 months of alloHSCT. The primary endpoint of this study is the hematologic CR/CRh* rate within 2 cycles of treatment with blinatumomab. This prespecified endpoint was met if > 30% of subjects achieved a CR/CRh* during this time interval. Subjects who have achieved CR or CRh* within 2 cycles of treatment can receive up to 3 additional cycles of maintenance treatment or proceed to BM transplantation. Key efficacy endpoints include RFS, duration of complete remission, proportion of subjects eligible for alloHSCT who undergo the procedure after blinatumomab treatment, and rate of MRD response (defined as MRD < 1 x 10⁻⁴ leukemic cells detectable measured by PCR) within 2 cycles of blinatumomab treatment.

A total of 189 subjects were enrolled and received ≥ 1 infusion of blinatumomab. All 189 subjects were included in the Primary Analysis Set (PAS) and Full Analysis Set

(FAS). Overall, most subjects were men (63.0%) and white (85.8%), with a median age (range) of 39 years (range 18 to 79 years). Approximately 41% of subjects received blinatumomab as third-line treatment, and 39% received it as fourth-line or greater; the remaining 20% of subjects were either primary refractory or had relapsed within 12 months of first remission. One-hundred thirty subjects (68.8%) had a BM blast count of 50% at baseline based on central laboratory assessments.

In the PAS, the rate of CR/CRh* within the first 2 treatment cycles was 42.9% (81/189; 95% CI: 35.7, 50.2). Since the lower bound of the 95% CI was > 30%, the remission rate was significantly greater than 30%.

The best response rates including the rates of CR/CRh* during the first 2 cycles are provided in Table 6. Three subjects who had achieved a CRh* response at the end of 2 cycles of treatment converted to CR by the end of the core study and one subject converted from a non-response to a CR, resulting in an overall CR rate of 35.4% for the core study.

Table 6. Best Response During the First 2 Cycles of Treatment in Study MT103-211

Best Response	PAS (N = 189)		
	n	(%)	95% CI

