Amendment Date: 20 February 2018

Rationale:

This protocol is being amended to:

- Increase the number of participating sites from 20 to 25
- Update Exclusion criteria 221 to align with program level contraceptive language
- Update Exclusion criteria 209 to align with the instruction to calculate eGFR
- Replace local Safety Review Committee with Data Review Team
- Add a time window for PK sample collection
- Incorporate updated blinatumomab program level guidelines for
 - Dose Modifications (Interruptions, Withholdings, and Criteria for Restarting Treatment)
 - Criteria for Conditional Withholding of Blinatumomab and Other Protocol-required Therapies due to Potential Hepatotoxicity
- Remove serum cytokine concentrations from secondary endpoints
- Add quantification and characterization of serum cytokines and chemokines to exploratory endpoints
- Move 100-day mortality after alloHSCT from safety endpoints to secondary endpoints
- Clarify visit window for long term follow-up
- Remove references to maintenance phase as there is no maintenance phase for this study
- Clarify dexamethasone dose for CNS-related adverse events

Amendment 01

**Protocol Title: An Open-label, Multicenter, Phase 3 Study to Evaluate Efficacy and Safety of the BiTE® Antibody Blinatumomab in Chinese Adult Subjects With Relapsed/refractory B-precursor Acute Lymphoblastic Leukemia (ALL)
Blinatumomab**

Amgen Protocol Number (Blinatumomab) 20130316

Date: 29 July 2015
Amendment Date: 07 December 2016

Approved

Rationale:

The following changes are being made to the study for the reasons indicated:

- The Chinese Food and Drug Administration (CFDA) is open to have interim analysis in our study for early NDA filing which was discussed at CDE formal consultation meeting in March 2016.
- The interim analysis is planned at 75% (90 subjects) enrollment, strong efficacy is provided at IA by using OBF alpha-spending function where CR/CRh* rate has to be equal to or greater than 42.2%.
- In terms of safety, although study may have the chance for early NDA filing at the time of interim analysis, the study won't stop enrollment and will continue to enroll the remaining 30 patients. The 120 subjects' safety data will be provided to CFDA.
- Change in exploratory objectives and endpoints: the acute lymphoblastic leukemia symptom scale (ALLSS) was removed as this scale was not validated.

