3.2 Sample Size

The overall sample size of 120 subjects, calculated using the exact method for a single proportion, was estimated in order to ensure 90% power to detect a significant difference in terms of CR/CRh* rate between historical control with 30% CR/CRh* rate and blinatumomab assuming 45% CR/CRh* rate in the alternative hypothesis, at the 2.5% one-sided significance level.

4. Study Endpoints and Covariates

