8.1 Interim Analysis and Early Stopping Guidelines

The interim analysis will assess blinatumomab efficacy and safety and will be based on the Interim Analysis Set. The efficacious benefit assessment will be based on an O'Brien-Fleming alpha spending function (O'Brien and Fleming, 1979) with the critical boundary 42.2% at the interim analysis and 39.2% at the primary analysis in CR/CRh*

rate. If the interim analysis showed statistically efficacious and overall benefit-risk analysis is promising, then the interim analysis will become the primary analysis of this study. In addition, the study will still continue its enrollment until 120 subjects are enrolled and continue to complete the protocol specified procedures.

The interim analysis will be reviewed by an Amgen internal Data Review Team (DRT) including medical scientist, biostatistician, safety scientist, pharmacologist. The interim analysis will be performed by the independent biostatistician and the programmers supporting the DRT. The DRT and independent biostatistician and programmer are independent from the Clinical Study Team, which allows the study integrity to be maintained. The DRT will also review safety data at the time of interim analysis.

Additional ad hoc Interim Analyses may be performed descriptively without alpha spending. Pharmacokinetic samples collected at specific timepoints may be analyzed and reported. The purpose of this analysis is just to provide descriptive analyses of PK, safety, and efficacy information (including 95% confidence intervals) for regulatory submissions and interactions.

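### The final success boundary of 39.2% has no responder count, inequality or rounding rule, so whether 47/120 succeeds depends on how the comparison is made

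*Protocol*

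**What the plan says.** Protocol 10.3.1 sets the efficacy decision by an O'Brien-Fleming alpha spending function with "critical boundary 42.2% at the interim analysis and 39.2% at the primary analysis in CR/CRh* rate". The protocol synopsis has the same text, and SAP 8.1 repeats it: "critical boundary 42.2% at the interim analysis and 39.2% at the primary analysis". None of the three places gives a number of responders, says whether the rate must reach or exceed the boundary, or says to how many decimals the observed rate is taken before the comparison.

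Protocol 10.2 describes 120 subjects as "calculated using the exact method for a single proportion, was estimated in order to ensure 90% power", for 30% against 45%, "at the 2.5% one-sided significance level". SAP 3.2 says the same ("calculated using the exact method for a single proportion"). The primary result is the response rate with an exact 95% confidence interval (protocol 10.4.2, SAP 10.5.1).

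The only inequality is in the Amendment 1 rationale at the end of the protocol: "CR/CRh* rate has to be equal to or greater than 42.2"%. That is amendment-log text and covers the interim boundary only. It is cited here as context, not as an error.

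**The concern.** The printed percentage is the decision threshold for the primary endpoint. The critical count implied by the stated design is 47 of 120, which is 39.167%. Printed to one decimal this becomes 39.2%, and 39.2% of 120 is 47.04. A program that compares the unrounded rate with 0.392 therefore rejects a result that the stated design counts as success. A reader who rounds the observed rate first accepts it. The documents do not choose between the two, and in an open-label single-arm trial that choice should not be left until the data are known.

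**Working it through.** **Inputs.** Null rate 0.30, alternative 0.45, one-sided alpha 0.025, N = 120, exact method (protocol 10.2, SAP 3.2). Interim at 90 subjects, information fraction 0.75, O'Brien-Fleming spending (protocol 10.3.1, SAP 7.4 and 8.1). The Lan-DeMets form of the spending function is an assumption; the documents do not give the formula.

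**Step 1. The stated 90% power.** Single look, exact binomial, n = 120:
- at least 46: P(X ≥ 46 | 0.30) = 0.0312, above 0.025
- at least 47: P(X ≥ 47 | 0.30) = 0.0200; P(X ≥ 47 | 0.45) = 0.916

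The critical count is 47 and power is 91.6%, so the stated 90% is met.

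**Step 2. Interim count.** Spend at t = 0.75: 2[1 − Φ(z₀.₉₈₇₅/√0.75)] = 0.00965.
- P(X ≥ 37 | 90, 0.30) = 0.01623, too large
- P(X ≥ 38 | 90, 0.30) = 0.00922, fits

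38/90 = 42.22%, which reproduces the printed 42.2%.

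**Step 3. Final count.** With 38/90 at the interim and final count c,

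P(success | p) = P(X₁ ≥ 38) + Σ over x < 38 of P(X₁ = x) · P(X₂ ≥ c − x), with X₁ ~ Bin(90, p) and X₂ ~ Bin(30, p).

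| c | c/120 | Type I error (p = 0.30) | Power (p = 0.45) |
|---|---|---|---|
| 46 | 38.33% | 3.29% | 94.3% |
| 47 | 39.167% | 2.27% | 92.0% (73.7% interim + 18.3% final) |
| 48 | 40.00% | 1.64% | 89.3% (73.7% interim + 15.6% final) |

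47 is the smallest count that keeps type I error within 2.5%, and 47/120 rounds to the printed 39.2%.

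**Step 4. Is the source of 39.2% certain?** No, because no count is printed. A classic O'Brien-Fleming normal approximation with the variance at 45% gives 42.20% and 39.15%, which also round to the printed pair. 39.15% of 120 is 46.98, so this source admits 47/120 before rounding as well.

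**Step 5. Apply the printed figures to unrounded rates.**
- Interim: 0.422 × 90 = 37.98. 38/90 passes and 37/90 (41.11%) fails, whether or not the rate is rounded.
- Final: 0.392 × 120 = 47.04. 47/120 fails and 48/120 passes. If the observed rate is first rounded to one decimal, 47/120 becomes 39.2% and passes.

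**Step 6. Compare with the planned interval.** The exact 95% lower limit is 30.4% at 47/120 and 29.6% at 46/120. At 47/120 the interval excludes 30%, while the boundary applied to the unrounded rate says failure.

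**Step 7. How often it matters.** P(X₁ < 38 and total exactly 47) is 6.0% at a true rate of 38%, 6.2% at 39%, 6.1% at 40% and 2.7% at 45%. At 40% the chance of success is 61.9% with 47 and 55.8% with 48.

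**Step 8. If the analysed N is not 120.** Keeping 38/90 and total alpha 2.5%, the smallest valid final count is 47 at N = 119, 48 at N = 121 and 48 at N = 122. The unrounded 39.2% rule gives the same counts there (46.65, 47.43 and 47.82, rounded up). At N = 123 the valid count is again 48, but 0.392 × 123 = 48.22 requires 49. The mismatch depends on N and is present at the planned 120.

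**The case against.** The strongest reply is that nothing is miscalculated. 47/120 to one decimal is 39.2%, and the protocol prints response rates to one decimal elsewhere, as in "the rate of CR/CRh* within the first 2 treatment cycles was 42.9% (81/189"), where the unrounded value is 42.857%. On that convention 47/120 meets the boundary. The rule is also said to rest on the spending function, and a statistician applying it by the exact method arrives at 47. The planned interval points the same way: protocol 2.5.2 treats a lower limit above 30% as significance for the earlier phase 2 study. Finally, enrolment is only approximately 120, so a percentage is a natural way to print a boundary.

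Most of this stands. Three stronger readings are tempting, and the documents do not support them:
- **That 39.2% is an arithmetic error.** It is a correct rounding of the apparent critical rate.
- **That 47/120 fails under the plan.** It fails only if an unrounded rate is set against the rounded boundary, and the plan does not prescribe that.
- **That the trial is underpowered.** The stated 90% is described as a single-proportion calculation without mention of the interim, and it is met at 91.6%. The 89.3% belongs to the two-stage rule under the less favourable comparison.

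The reply does not supply the missing rule. A printing convention for results is not a decision rule, and neither document says whether the boundary or the interval governs if they disagree.

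**Conclusion.** The point holds as an ambiguity in the decision rule for the primary endpoint. On one permissible comparison the printed boundary rejects 47/120, which the stated design and the planned exact interval both count as success. The cost on that comparison is 2.7 points of two-stage power (92.0% to 89.3%) and a type I error of 1.64% instead of 2.27%. On the other comparison there is no loss.

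The consequence is one responder and can only be conservative, since type I error stays below 2.5% either way. At a true rate of 45% the interim alone succeeds with probability 73.7%, so the question usually does not arise.

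This rests on 38/90 at the interim, on exactly 120 analysed subjects, and on the inference in steps 2 to 4 that 39.2% stands for 47/120. Severity: minor.

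**What to change.** In the protocol synopsis, protocol 10.3.1 and SAP 8.1, state success as at least 38 responders among 90 at the interim analysis, or at least 47 among 120 at the primary analysis. The percentages can stay in brackets as rounded values. Add that if the analysed N is not 120, the final critical count is recomputed by exact binomial from the stated alpha-spending function, given the interim rule already used.

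The cost is one sentence in each of three places, with no extra patients and no new analyses. With these counts the boundary and the exact interval agree at 47/120, with power 92.0% and type I error 2.27%.
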